# **3.2** Collect the following data:

(1) Demography: sex, age, height, weight

(2) Vital signs: SOFA score and APACHE II score were measured 24 hours after admission to ICU and randomness.

(3) Physiological and biochemical indexes: blood routine, blood biochemistry (total protein, ALB, total bilirubin, AST, ALT, GGT, blood urea nitrogen, serum creatinine), TNI, BNP, CRP before APRV, APRV24h, 48h, 72h and at the end of APRV24h.
(4)Respiratory mechanical parameters before APRV, APRV6h, 12h, 24h, 48h, 72h

and end APRV24h.

(5)Cardiac ultrasound and hemodynamic indexes before, after, and after APRV at 6, 12, 24, 48, 72, and 24h.

(6)Fatality rate at 28 days after inclusion, length of stay in ICU, length of stay, and

fatality rate in hospital.

# 3.3 Sample size

This study is to study the effect of APRV on right heart function. Referring to previous literatures, the number of subjects is generally required to be 40, and the number of subjects should be increased to 50 in consideration of shedding and withdrawal, etc.

# 4.Study population

# 4.1 Diagnostic criteria

According to the Berlin 2012 ARDS diagnostic criteria

# 4.2 The inclusion criteria

(1). Patients who met the 2012 Berlin ARDS diagnostic criteria and underwent invasive mechanical ventilation

(2). PEEP≥5cmH2O, oxygenation index ≤200mmHg

(3). The duration of endotracheal intubation and mechanical ventilation was less than48h at the time of inclusion

(4). Age  $\geq 18$  and  $\leq 80$  years old

# 4.3 Exclusion criteria

- (1). Younger than 18 years old or older than 80 years old
- (2). BMI of obese patients  $\geq$  35kg/m2;
- (3). Pregnant and lactating women
- (4). The expected time of invasive mechanical ventilation is less than 48h
- (5). Neuromuscular diseases known to require prolonged mechanical ventilation
- (6). Severe chronic obstructive pulmonary disease
- (7). Intracranial hypertension

(8). Pulmonary bullae or pneumothorax, subcutaneous emphysema, mediastinum emphysema

(9). ECMO treatment was performed when admitted to ICU

(10). Refractory shock

(11). Severe cardiac dysfunction (New York Heart Association Class iii or iv, acute coronary syndrome or persistent ventricular tachyarrhythmia), enlargement of the right heart due to chronic cardiopulmonary disease, cardiogenic shock or major cardiac surgery;

(12). Informed consent was not signed

Note: All subjects meeting either of the exclusion criteria at baseline will be excluded from the study

# 5. The items and frequency of clinical and laboratory examinations to be performed

Cardiac ultrasound examination was performed before APRV mechanical ventilation, 6h, 12h, 24h, 48h, 72h after APRV mechanical ventilation, and 24h after APRV mechanical ventilation. Mechanical ventilation parameters were recorded, respiratory mechanics and arterial blood gas analysis were measured, and hemodynamic indexes were recorded.

Collect the following data:

(1). Demography: sex, age, height, weight

(2). Vital signs: 24h SOFA score and APACHE II score after admission to ICU and randomization

(3). Physiological and biochemical indicators: echocardiographic right heart function monitoring, hemodynamic parameters and arterial blood gas were performed before APRV or LTV mechanical ventilation, 6h, 12h, 24h, 48h, 72h after mechanical ventilation, and 24h after mechanical ventilation.

(4). Blood routine examinations, blood biochemistry (total protein, ALB, total bilirubin, AST, ALT, GGT, blood urea nitrogen, serum creatinine), TNI, BNP and CRP were performed at 24, 48 and 72 hours after admission to ICU and randomization.

()Respiratory mechanical parameters before and after randomization at 24h, 48h and 72h.

Case fatality rate at 28 days after inclusion, length of stay in ICU, length of stay, and in-hospital case fatality rate.

# 6.evaluation

#### 6.1Primary and secondary end point/outcome evaluation

Primary endpoint: Effect of APRV mechanical ventilation for 24 hours on right heart function in ARDS patients

Secondary endpoint: Effects of APRV ventilation at other time points on right heart function in ARDS patients.

Effects of APRV ventilation at different time points on hemodynamics of ARDS patients.

Mortality rate of ARDS patients on APRV mechanical ventilation at 28 days after enrollment, length of stay in ICU, length of stay, and mortality rate in hospital.

#### 6.2 Safety evaluation

APRV mechanical ventilation is a mode of mechanical ventilation for

ARDS patients, which has been proved to be safe in animal and clinical studies.

#### 7.Adverse events and serious adverse events

Adverse event reports: Adverse medical events that occur in patients receiving mechanical ventilation with APRV, but are not necessarily causally related to treatment.

Reports of serious adverse events: events requiring hospitalization, prolonged hospitalization, disability, inability to work, life threatening or death occurred during APRV mechanical ventilation. During a clinical trial, the clinical investigator is obligated to take necessary measures to ensure the safety of the subject and to document them.Such as serious adverse events during the process of clinical trials, researchers should immediately treatment for participants to take appropriate measures, and report by phone or fax within 24 hours of the main researchers, the clinical test units of ethics committee, the province, municipality directly under the central government or autonomous region food and drug administration and the state food and drug administration and bidders.At the same time, a written report shall be submitted to the above institutions within 15 days.All serious adverse events must be completed in the CRF Serious adverse Event Report Form.

All serious adverse events should be followed up until resolved, returned to baseline, and proved unsolvable/ Permanent, change to other treatment, or death. Medical documentation of serious adverse events should be documented in the original documentation and follow-up tables, including results of laboratory and ancillary tests.

The investigator and other responsible persons should analyze and determine the causal relationship between serious adverse events in the subjects from a clinical perspective.

#### 8. Statistical analysis and statistical methods

Prism 4.01 was used for statistical analysis software.Because all the parameters are non-normally distributed, the data is represented as the median (quartile range;Head).Friedman ANOVA of repeated measurements was used to compare the data obtained at each step and, where appropriate, through Dunn post hoc tests using Bonferroni correction.Qualitative data were compared with Fisher's exact test.All comparisons were double-tailed, with P<0.05 indicating the existence of significant differences.

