#### 1.1.3 Research Basis

ARDS is often complicated with RVD, and the incidence can be as high as 64%. ARDS patients with RVD have a worse prognosis and a significantly higher risk of death, which is an independent risk factor for death in ARDS patients. Randomized controlled studies have shown that compared with low tidal volume ventilation, APRV can increase average airway pressure [7], which may theoretically increase intrathoracic pressure and extrapericardial pressure, thereby affecting venous return, increasing pulmonary circulation resistance, leading to right heart dysfunction and even hemodynamic deterioration. However, the actual effect of APRV on right heart function in ARDS patients has not been reported.

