#### 2. Study Objective/end point

**Objective**: To study the effect of APRV on right ventricular function in ARDS patients.

**Primary endpoint/outcome**: Effect of APRV mechanical ventilation for 24 hours on right heart function in ARDS patients.

**Secondary end point/outcome**: Effects of APRV ventilation at 6h, 12h, 48h, 72h and 24h after APRV ventilation on right heart function in ARDS patients.

Effects of APRV ventilation at 6h, 12h, 24h, 48h, 72h and 24h after APRV ventilation on hemodynamics of ARDS patients.

Mortality rate of ARDS patients on APRV mechanical ventilation at 28 days after enrollment, length of stay in ICU, length of stay, and mortality rate in hospital.

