# 9.2 Medical treatment and protection of subjects during the study

The rights and welfare of the subjects will be protected during the study, and the quality of their medical care will not be affected by their refusal to participate or withdrawal from the study.

If the patient drops out of the study, we will no longer conduct study related tests.

The investigator will provide insurance for the subjects participating in the study program. If the subjects suffer any damage related to the study, they will receive timely and free treatment and be compensated or compensated according to laws and regulations and mutual agreements.

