# 10.5 Data processing and record keeping

#### 10.5.1 Data collection and management

The required data were collected from medical records of patients who met the inclusion criteria and filled in paper case reports(CRF).

Data collection will be carried out by clinical researchers under the supervision of the director, who will be responsible for the accuracy, completeness and timeliness of the reported data.All data shall be clear to ensure accurate interpretation and traceability.

Data entry: Remote data entry shall be carried out after the training of data entry staff, which shall be completed by two persons independently by using the double-copy entry method.

Data review: Manual comparison of data in the case report form and the database to ensure that the data in the database are consistent with the results in the case report form.

Data locking: In addition to the above data review, the principal investigator, statistician, data manager and sponsor representative shall further discuss and confirm the main content of the study proposal and the statistical analysis proposal.Conduct audit to confirm that all data have been entered into the database, all questions have been resolved, and the analysis group has been defined and judged before locking the data.

Clinical data will be stored in a database, which shall be password protected and logical proofreading procedures shall be set up when the database is established.

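### A Friedman test over all seven echoes drops patients from the 24 h primary comparison although both of their primary echoes were recorded

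*Protocol*

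**What the plan says.** Section 8 names one method for repeated quantitative data: "Friedman ANOVA of repeated measurements was used to compare the data obtained at each step", with Bonferroni-corrected Dunn tests afterwards where appropriate. It does not define a step and names no separate test for the primary endpoint. Fisher's exact test is reserved for qualitative data.

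The primary endpoint in section 2, repeated in section 6.1, is "Effect of APRV mechanical ventilation for 24 hours on right heart function in ARDS patients". Section 2 places the right heart results at 6, 12, 48 and 72 h and at 24 h after APRV among the secondary endpoints.

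The schedule in section 5 reads: "Cardiac ultrasound examination was performed before APRV mechanical ventilation, 6h, 12h, 24h, 48h, 72h after APRV mechanical ventilation, and 24h after APRV mechanical ventilation". Section 3.2 lists the same times. That makes seven echoes, of which two serve the primary comparison.

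Three other places bear on missing echoes:

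- Section 3.3 asks for 40 patients and adds that "the number of subjects should be increased to 50 in consideration of shedding and withdrawal".
- Section 9.2 says: "If the patient drops out of the study, we will no longer conduct study related tests".
- Section 10.5.1 requires that "the analysis group has been defined and judged before locking the data", but does not say who belongs to that group.

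**The concern.** The Friedman statistic ranks all time points within a patient, so a patient with a gap is not a usable block. The Dunn comparisons use the same ranks and do not bring the patient back. The protocol states no complete-case rule, but the test it names imposes one.

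Over seven steps, a patient with valid pre-APRV and 24 h echoes leaves the primary comparison because of a gap at 6, 12, 48 or 72 h, or at 24 h after APRV. The last three can be missing through death, withdrawal or the course of weaning, and a patient who dies on APRV cannot have the post-APRV echo at all. Who counts in a 24 h result then depends partly on what happens after 24 h.

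Two things are at stake. Primary data already collected are thrown away. And if the patients lost differ in their 24 h change, the result is biased: losing the sickest hides a worsening, losing those weaned early exaggerates it. The protocol's own premise makes a link plausible, since section 1.1.3 states that "ARDS patients with RVD have a worse prognosis and a significantly higher risk of death, which is an independent risk factor for death" in ARDS.

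**Working it through.** **The plan's own figure.** Section 3.3 goes from 40 to 50 without a loss rate. 40/50 = 0.80, so the step corresponds to a 20% loss: 40/(1 − 0.20) = 50. The 40 cannot be reproduced, because no effect size, SD or power is given. The check below takes 50 enrolled and 40 required as they stand.

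**Complete-block property.** In a simulated 50 × 7 data set with one value missing in 15 patients, a standard routine (scipy) returned no result by default. Told to omit missing values, it gave exactly the result from the 35 complete patients (statistic 6.196, p = 0.402).

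**Patients retained.** Assume that each post-baseline echo is missing independently with probability m and that the pre-APRV echo is always present. The protocol gives no value for m.

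| | Formula | m = 2% | m = 5% | m = 10% |
|---|---|---|---|---|
| Both primary echoes | 50(1 − m) | 49.0 | 47.5 | 45.0 |
| All four echoes to 24 h | 50(1 − m)³ | 47.1 | 42.9 | 36.5 |
| All seven echoes | 50(1 − m)⁶ | 44.3 | 36.8 | 26.6 |
| Interval width, seven-step against pairs | (1 − m)^(−2.5) | 1.05 | 1.14 | 1.30 |

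The width ratio is √[50(1 − m) / 50(1 − m)⁶], taking width as proportional to 1/√n.

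**How fast the allowance is used up.** The expected number complete falls to 40 when the retained fraction is 0.8:

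- seven steps: (1 − m)⁶ = 0.8, m = 3.7%
- four steps: (1 − m)³ = 0.8, m = 7.2%
- primary pair only: 1 − m = 0.8, m = 20%

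**Clustered gaps.** Suppose instead that patients leave for good, with probability m at each visit. Complete series stay at 50(1 − m)⁶, but 24 h pairs fall to 50(1 − m)³. The width ratio becomes (1 − m)^(−1.5) = 1.03, 1.08 or 1.17. If all gaps fall in patients who also lack the 24 h echo, the excess loss is zero.

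**Bias.** Assume a true mean change of −0.40 SD (SD of the change), 50 patients and 10 lost by rank on a variable with correlation ρ to the change. Mean change in the 40 retained, from 40,000 simulated trials:

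| Lost from worst / best end | ρ = 0 | ρ = 0.25 | ρ = 0.5 |
|---|---|---|---|
| 10 / 0 | −0.400 | −0.314 | −0.229 |
| 8 / 2 | −0.400 | −0.352 | −0.302 |
| 5 / 5 | −0.400 | −0.400 | −0.400 |
| 2 / 8 | −0.400 | −0.449 | −0.497 |
| 0 / 10 | −0.400 | −0.486 | −0.571 |

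As a check, the large-sample shift with all losses at one end is ρ·φ(z at 0.2)/0.8, which gives 0.087 at ρ = 0.25 and 0.175 at ρ = 0.5. This agrees with the first and last rows.

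A second simulation used another selection model: true change zero, log-odds of loss falling by 0.5 or 1 per SD of change, 21% or 24% lost. The retained mean shifted by 0.10 or 0.20 SD, and the false-positive rate of a two-sided 5% paired test rose to about 9% or 23%. With loss unrelated to the change, it stayed near 5%.

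**The case against.** The strongest reply is that missing visits, analysis sets and the exact primary contrast usually belong in the SAP, which is not at hand. Section 10.5.1 mentions a statistical analysis proposal still to be confirmed. That would answer a complaint that a rule is absent. The complaint here is that section 8 positively names a test that cannot use incomplete patients. A SAP might repair this, but section 8 as written would still need correcting.

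Second, a step is undefined, and the test might run only up to 24 h. On that reading no event after 24 h decides who counts, and permanent dropout removes nobody who has a 24 h echo. The more serious part of the concern would then fall away. A sporadic gap at 6 or 12 h would still cost a patient. The seven-step reading remains the natural one, because no narrower scope is given and a two-point Friedman test would leave the Dunn step with nothing to do.

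Third, the rates and correlations come from no document, and section 1.1.3 does not say that the 24 h change predicts a missing echo. That stands: the figures show what could happen, not what will. Death and withdrawal also give permanent rather than sporadic loss, so the smaller width penalties of about 3%, 8% and 17% fit those causes better. Section 8 reports medians and rank tests, so interval widths and mean shifts serve only as measures of precision and bias.

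Finally, a paired test still omits patients who die or withdraw before the 24 h echo. That is true; the proposal removes only the avoidable loss.

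**Conclusion.** The concern holds as a conditional statement. If the Friedman/Dunn analysis spans all seven echoes, patients with both primary echoes are discarded because of gaps that have nothing to do with the primary endpoint. With assumed missingness of 2% to 10% per post-baseline echo, the cost is an interval about 5% to 30% wider if gaps are independent, 3% to 17% if they come from permanent dropout, and nothing if they coincide with a missing 24 h echo.

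Bias arises only if the loss is related to the 24 h change. With 10 of 50 lost from one end, it is about 0.09 SD at correlation 0.25 and 0.17 SD at 0.5, in either direction. It is zero if the loss is unrelated or balanced. The documents establish neither a loss rate nor such a correlation.

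This should be fixed. Confidence is moderate, because the scope of the test is inferred from section 8 and an unseen SAP may narrow it.

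**What to change.** In section 8, name the primary analysis as a paired comparison of the pre-APRV and 24 h echoes, for example a Wilcoxon signed-rank test, in every patient who has both, whatever happened at other visits. Keep the Friedman test with Dunn comparisons as a secondary analysis of the time course, and say which steps it covers. Report the number of missing echoes at each time with the reasons, including patients without a 24 h echo, whom the paired test cannot recover. A time-course method that keeps incomplete patients may be added but is not essential.

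The cost is a few sentences in section 8 and a little analysis work. No further patients or measurements are needed.

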Studies have shown that APRV can improve oxygenation and is very safe compared with lung protective ventilation with low tidal volume [6]. It is worth noting that randomized controlled studies have shown that APRV can increase average airway pressure compared with low tidal volume ventilation [7], which may theoretically increase intrathoracic and alveolar pressure, increase external pericardium pressure, thereby affecting venous return, increasing pulmonary circulation resistance, and leading to right heart dysfunction and even hemodynamic deterioration.However, the actual effect of APRV on right heart function in ARDS patients has not been reported.In this study, transthoracic cardiac ultrasound was used to evaluate right heart function, pulmonary artery pressure, tricuspid regurgitation and hemodynamics related indicators in ARDS patients receiving APRV mechanical ventilation, so as to fully understand the influence of APRV mechanical ventilation mode on right heart function and hemodynamics, which is more conducive to clinical application and avoid the occurrence of adverse reactions.

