# 3.Study design

# 3.1 Overall Design

(1). A single center prospective observational study.

(2).In ARDS patients receiving APRV mechanical ventilation, right heart function was monitored at 6, 12, 24, 48, 72 hours after APRV mechanical ventilation, and 24 hours after APRV mechanical ventilation. Mechanical ventilation parameters, respiratory mechanics and arterial blood gas analysis were recorded, and hemodynamic indexes were recorded at the same time.

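### The primary endpoint, the 24 h effect on right heart function, names no echocardiographic index, change measure or reference time; section 8 also does not single out the 24 h contrast

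*Protocol*

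**What the plan says.** Section 2 gives the primary endpoint as "Effect of APRV mechanical ventilation for 24 hours on right heart function in ARDS patients", and section 6.1 repeats it without adding anything. Neither section names a measured variable, a form of change or the time against which 24 h is compared.

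The other sections do not fill the gap:

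- Section 1.1.1 gives domains only: "transthoracic cardiac ultrasound was used to evaluate right heart function, pulmonary artery pressure, tricuspid regurgitation and hemodynamics related indicators in ARDS patients". Section 1.3 repeats them.
- Section 3.2 lists "Cardiac ultrasound and hemodynamic indexes before, after, and after APRV at 6, 12, 24, 48, 72, and 24h", with no parameter named.
- Section 5 speaks of "echocardiographic right heart function monitoring, hemodynamic parameters and arterial blood gas were performed before APRV or LTV mechanical ventilation". (The second ventilation mode mentioned there is a separate matter.)
- The scan times are clearest in section 5: "Cardiac ultrasound examination was performed before APRV mechanical ventilation, 6h, 12h, 24h, 48h, 72h after APRV mechanical ventilation, and 24h after APRV mechanical ventilation". Section 3.1 says that "right heart function was monitored at 6, 12, 24, 48, 72 hours after APRV mechanical ventilation" and then adds the scan 24 h after APRV; it lists no scan before APRV. The reference time must therefore be inferred from sections 3.2 and 5.

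Section 8 sets one scheme for all repeated data. Friedman's test is "used to compare the data obtained at each step and, where appropriate, through Dunn post hoc tests using Bonferroni correction", with all comparisons two-sided at 0.05. It does not single out the 24 h contrast, state which pairs are corrected, or correct across different indices.

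**The concern.** What the primary endpoint measures belongs in the protocol. Bedside echocardiography can yield several right-heart measures, and they need not agree. If none is named, any of them can be presented as the primary result once the results are known, and the reader of the report cannot tell a planned primary result from a selected one. Section 8 corrects across time steps within a variable, and that does nothing about choice between variables.

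The second, lesser matter is how the 24 h question is tested. A single prespecified contrast needs no multiplicity correction. In section 8 it is reached only as one possible post hoc pair, so a true 24 h change may be easier to miss than the primary question requires.

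**Working it through.** **Inputs from the protocol.** Seven scans (section 5): before APRV, at 6, 12, 24, 48 and 72 h, and 24 h after APRV. Two-sided 0.05 (section 8). Forty subjects, raised to 50 for losses (section 3.3).

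**The plan's own figure.** The step from 40 to 50 fits an assumed 20% loss: 40 / (1 − 0.20) = 50. The 40 itself cannot be reproduced, because no index, effect size, SD or power is given. The protocol therefore has no power figure for the 24 h contrast, and every power below is illustrative.

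**Choice among indices.** Assume three indices, none of which changes, each tested by Friedman at 0.05. If they are independent, the chance of at least one significant result is 1 − 0.95³ = 14.3%. Simulation with inter-index correlation 0 to 0.5 gives about 13–14%. The chance that at least one of the three shows a significant corrected 24 h Dunn test after a significant Friedman test is much lower: 0.5–0.7% with 21 pairs and 1.1–1.5% with 6 pairs. If the 24 h pair were instead tested without correction by a Wilcoxon test on each of the three, the chance would be about 12–14%.

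**Threshold for the 24 h contrast.** Seven scans give 7 × 6 / 2 = 21 pairs, or 7 − 1 = 6 comparisons with baseline. The per-pair level is 0.05 / 21 = 0.00238 or 0.05 / 6 = 0.00833, against 0.05 for one test.

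**Detectable change by normal approximation.** With n = 40 and an assumed 80% power, the detectable change, in SDs of the paired difference, is (z for the two-sided level + z for 80% power) / √40:

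- One test: (1.960 + 0.842) / 6.325 = 0.44
- Six pairs: (2.638 + 0.842) / 6.325 = 0.55
- Twenty-one pairs: (3.038 + 0.842) / 6.325 = 0.61

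For a true change of 0.44 SD, power falls from 80% to about 57% (6 pairs) or 41% (21 pairs).

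**Simulation of the section 8 scheme.** Assumptions: n = 40 with all seven scans, within-patient correlation 0.6, and a 24 h change of 0.45 SD of the paired difference. Three time courses were used (plateau, ramp, peak), and the ranges span them. Skewed errors are lognormal with log-SD 0.5 (moderate) or 1 (strong). Dunn's statistic is z = |R₂₄ − R₀| / √(n·k·(k + 1) / 6), where R₂₄ and R₀ are the rank sums at 24 h and before APRV and k = 7. It is used only after Friedman P < 0.05.

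| Errors | Single Wilcoxon | Dunn, 24 h pair only | Dunn, 6 pairs | Dunn, 21 pairs |
|---|---|---|---|---|
| Normal | 77–78% | 60–71% | 43–47% | 29–32% |
| Moderate skew | about 86% | 85–88% | 68–72% | 52–57% |
| Strong skew | 98% | at least 98% | 98–100% | 95–99% |

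Without the preliminary Friedman step, normal errors give 46–48% (6 pairs) and 29–32% (21 pairs), so the correction causes most of the loss. At a smaller change of 0.3 SD under strong skew, the figures are 85% for Wilcoxon against 84–92% (6 pairs) or 71–84% (21 pairs).

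**The case against.** The case against the testing point is strong, and most of it stands. Which pairs Bonferroni covers is detail that a statistical analysis plan can supply, and section 10.5.1 refers to a statistical analysis proposal. Friedman with corrected Dunn tests is a valid method for seven repeated scans, and pre-APRV against 24 h can be one of the pairs. The size of the power loss rests on assumed effect, correlation, skew, time course and number of pairs. Section 8 itself calls the parameters non-normal without saying how skewed they are. Two inferences are therefore not supported:

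- A reader might infer that section 8 is wrong, or that it makes the study underpowered at 24 h. The documents do not show this. They give no effect size, and the comparison runs from a large loss to a small gain.
- A reader might infer that false 24 h claims are likely. The corrected Dunn tests make them rare. The 13–14% concerns the Friedman tests. The 12–14% for uncorrected 24 h tests would arise only if the correction were dropped, which the protocol does not propose.

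On the index, it can be said that section 1.1.1 lists right heart function apart from pulmonary pressure, tricuspid regurgitation and haemodynamics, so those are not obvious candidates, and that three indices is an assumed number. This narrows the choice but does not make it. Nor does anything show that an index has been or will be picked after the fact; the text only leaves that open. A statement of the Dunn pairs in an analysis plan would not name the variable missing from sections 2 and 6.1.

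**Conclusion.** The main defect holds, and it rests on the text alone: the primary endpoint has no named index, change measure or reference time, and nothing limits choice among indices. The 13–14% shows the scale of that freedom only for three assumed unchanged indices judged by Friedman.

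The testing point is supporting and conditional. If 6 or 21 pairs are corrected, the 24 h contrast is tested more strictly than one prespecified question needs. At 0.45 SD this costs roughly 14 to 49 percentage points of power across normal and moderately skewed errors. Under strong skew there is little or no loss at that size of change. If only the 24 h pair counts, the loss is smaller with normal errors and nil with moderate skew. The point should be fixed, with high confidence about the unnamed index and less about the size of any power loss.

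**What to change.** In sections 2 and 6.1, before any echo data are examined, name one continuous right-heart echo index that the sponsor confirms is recorded at each scan. Define the primary outcome as its change from pre-APRV to 24 h. If echo data have already been looked at, say so, because the naming would then itself be post hoc.

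In section 8, test that change once by a paired Wilcoxon signed-rank test at two-sided 0.05, and report the median change with a 95% CI. Keep Friedman and Bonferroni-corrected Dunn tests, with the compared pairs stated, for the other times and indices as secondary.

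The two changes belong together, since an uncorrected 24 h test without a named index would open the choice that the correction now restrains. The cost is a few sentences and no new data. The downside is that the other right-heart indices can no longer be claimed as primary.

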#### **1.1.2 Research Types**

Prospective single-center observational study

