#### **1.3 Discussion**

Acute Respiratory Distress Syndrome (ARDS) often complicated with Right Ventricular Dysfunction (RVD), and the incidence of RVD was as high as 64%.RVD often leads to low cardiac displacement and hemodynamic failure in patients.ARDS patients with RVD have a worse prognosis and a significantly higher risk of death, which is an independent risk factor for death in ARDS patients.

Mechanical ventilation is an important treatment for ARDS patients.Mechanical ventilation has a significant effect on hemodynamics by influencing right ventricular function through intrathoracic positive pressure, especially in patients with existing right ventricular insufficiency.

APRV is an inversely proportional mechanical ventilation mode with transient pressure release under continuous positive airway pressure (CPAP). APRV is commonly used in the treatment of ARDS patients. APRV improves oxygenation and is safe compared to low tidal volume lung protective ventilation and SIMV, but randomized controlled studies have not shown that APRV improves mortality. It is not clear whether the reason is related to APRV increasing average airway pressure [7], thus increasing pulmonary circulation resistance, leading to right heart dysfunction, or even hemodynamic deterioration. However, the actual effect of APRV on right heart function in ARDS patients has not been reported. In this study, transthoracic cardiac ultrasound was used to evaluate right heart function, pulmonary artery pressure, tricuspid regurgitation and hemodynamics related indicators in ARDS patients receiving APRV mechanical ventilation, so as to fully understand the influence of APRV mechanical ventilation mode on right heart function and hemodynamics, which is more conducive to clinical application and avoid the occurrence of adverse reactions.

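### Section 8 assigns Fisher's exact test to all qualitative data, but the one-cohort design defines only within-patient comparisons, so any yes/no finding compared between scans needs a paired test

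*Protocol*

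**What the plan says.** Protocol section 1.1.2 describes a "Prospective single-center observational study". Section 3.1 has one cohort, patients receiving APRV, in whom "right heart function was monitored at 6, 12, 24, 48, 72 hours after APRV mechanical ventilation" and again 24 h after APRV. Section 5 adds a scan before APRV. That makes seven scans per patient.

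Section 8 fixes two methods. For the time course, "Friedman ANOVA of repeated measurements was used to compare the data obtained at each step", followed by Bonferroni-corrected Dunn tests. For the rest, "Qualitative data were compared with Fisher"'s exact test. Nothing says which variables are qualitative or what is compared with what. Tests are two-sided at 0.05.

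The variables that might be qualitative are these:
- **Tricuspid regurgitation.** Sections 1.1.1 and 1.3 say that "transthoracic cardiac ultrasound was used to evaluate right heart function, pulmonary artery pressure, tricuspid regurgitation and hemodynamics related indicators". No scale is given.
- **Mortality.** Section 2 lists "Mortality rate of ARDS patients on APRV mechanical ventilation at 28 days after enrollment" and in-hospital mortality. Each is recorded once per patient in the single cohort.

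**The concern.** Fisher's exact test assumes two independent sets of patients, and this protocol defines none. Mortality and sex are single proportions with no comparator. The only comparisons described are before, during and after APRV in the same people. The unrestricted Fisher sentence therefore either has nothing to act on or would be applied to paired observations. Section 8 already uses a within-patient method for the time course of the measured parameters, so an independent-groups test for a yes/no version of the same time course would be out of step with it.

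The direction of the error matters. The study asks whether APRV harms the right heart. Treating 40 patients scanned twice as 80 unrelated patients discards the information on who changed. If the two scans of a patient tend to agree, p-values come out too large, and a real worsening is more likely to be reported as no significant change.

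**Working it through.** The plan has no figure of its own to reproduce here. Section 3.3 gives 40 patients, raised to 50, with no effect size, rate or power. The check therefore compares the two tests on the same paired data.

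**Inputs.** From the protocol: n = 40 (section 3.3), two-sided 0.05 (section 8), and 64% as one possible baseline rate (section 1.1.1, a literature maximum for right ventricular dysfunction). Assumed: all counts, the other baseline rates, the size of change, and the within-patient correlation. No multiplicity correction is applied to either test.

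**Worked table.** Finding present in 16 of 40 before APRV and 23 of 40 at 24 h, with 8 new and 1 resolved (16 + 8 − 1 = 23).
- Fisher sees 16/40 against 23/40, that is 39 positives among 80. P(X = x) = C(39, x)·C(41, 40 − x) / C(80, 40). With equal group sizes the two-sided p is 2·P(X ≤ 16) = 0.179.
- Exact McNemar sees only the 9 patients who changed: p = 2·[C(9,0) + C(9,1)] / 2⁹ = 20/512 = 0.039.

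**Second table.** 16 to 22 of 40, with 6 new and 0 resolved: Fisher 0.263; exact McNemar 2/2⁶ = 0.031.

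**Chance of p < 0.05.** All paired tables for n = 40 were enumerated. The model is a latent severity with between-patient SD 1 and within-scan SD √0.5. The SD of change is then √(0.5 + 0.5) = 1 and the scan-to-scan correlation is 1/1.5 = 0.67. The finding is present above a threshold set by its baseline rate, and every patient shifts by the stated amount.

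| Shift (SD of change) | Baseline rate | Fisher | Exact McNemar |
|---|---|---|---|
| 0 | 20 / 40 / 64% | 0.4 / 0.3 / 0.3% | 1.7 / 2.3 / 2.2% |
| 0.5 | 20 / 40 / 64% | 13 / 18 / 14% | 28 / 37 / 30% |
| 0.75 | 20 / 40 / 64% | 42 / 51 / 39% | 65 / 73 / 60% |

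With no effect both tests stay below 5%, so McNemar's gain does not come from excess false positives.

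**A second model.** The correlation is set directly on the yes/no outcomes, with rates 64% and 44%. At correlation 0.5, power is 31% (Fisher) against 61% (McNemar). At correlation 0.3 it is 34% against 47%.

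**Where the difference vanishes.** With zero within-patient correlation (40% to 57.5%), Fisher rejects in 29% and McNemar in 26%. With 64% at baseline, 30% new and 5% resolved, the figures are 71% and 74%.

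**The case against.** The strongest reply is that the protocol never says qualitative echo findings are compared between scans. Tricuspid regurgitation appears only in background and discussion text and could be a velocity or a grade. Right ventricular dysfunction is quoted as a literature incidence and is not an endpoint. Section 8 says that all parameters are non-normal and shown as medians, which points to numerical data. On this reading Friedman covers the time course, and the Fisher sentence is kept for comparisons between patients, such as survivors and non-survivors, where it would be valid. Detail on which variable gets which test can sit in an analysis plan.

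Part of this stands. No yes/no echo finding is named, so the number of affected results cannot be stated. What does not stand is the alternative use: no patient subgroup comparison is described anywhere. The test is also a stated choice with no limit on its scope, so the point is not merely about missing detail.

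Three stronger readings are tempting but unsupported:
- **That the primary 24 h result is tested wrongly.** Section 2 names no variable for it, and any numerical measure falls under Friedman.
- **That Fisher would create false positives.** With positively correlated scans the error runs the other way.
- **That there is a second arm which would justify Fisher.** Section 5 refers to assessments "performed before APRV or LTV mechanical ventilation" and to randomization, and section 3.2 has a similar stray term. This conflicts with the single-cohort observational design in sections 1.1.2 and 3.1, and no second group is otherwise described.

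**Conclusion.** The point holds conditionally. Section 8 fixes an independent-groups test for all qualitative data in a study whose only defined comparisons are within patients. If any yes/no finding is compared between scans, Fisher is the wrong test. When scans of the same patient agree, it is conservative: in the illustrations, power falls from 60–73% to 39–51% at a 0.75 SD shift, and p = 0.039 becomes 0.18 in the worked table. When they do not agree, the choice makes little difference.

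All these sizes rest on assumed counts, shifts and correlations, and 64% is not a rate for this cohort. The number of affected results is unknown and may be small. The Friedman and Dunn analysis is not in question. This is a worthwhile low-cost correction, not a threat to the study's main numerical analysis.

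**What to change.** Replace the Fisher sentence in section 8 with:

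*Any qualitative finding compared between scans in the same patients will be tested with the exact McNemar test (before APRV vs 24 h) and Cochran's Q across scans, with Bonferroni-corrected McNemar tests for other time points. Fisher's exact test will be used only to compare separate groups of patients. Mortality will be reported as a proportion with an exact 95% confidence interval.*

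The cost is one short paragraph, with no new patients, scans or data. McNemar needs each patient's status at both scans, not just the totals per scan, and the repeated scans already supply this.

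There are two downsides. Exact McNemar cannot reach p < 0.05 with fewer than 6 patients whose status changed (5 of 5 in one direction gives 2/2⁵ = 0.0625; 6 of 6 gives 0.031). Cochran's Q uses only patients with all scans. Neither test attributes a change to APRV, since there is no control arm.
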